5.3.2 Primary Outcome: Caregivers (CGs)

The SF-12 Health Survey (**SF-12**)²³ is a 12-item questionnaire that was developed as a shorter alternative to the SF-36.³¹ It consists of a subset of 12 items from the SF-36 Health Survey (SF-36) covering the same eight domains of health outcomes, including physical functioning (PF), role-physical (RP), bodily pain (BP), general health (GH), vitality (VT), social functioning (SF), role-emotional (RE), and mental health (MH). Physical and Mental Health Composite Scores (PCS & MCS) are computed using the scores of the twelve

questions and range from 0 to 100, where a zero score indicates the lowest level of health measured by the scales and 100 indicates the highest level of health. The SF-12 components have been demonstrated to be a reliable and valid measure, with multiple R^2 squares of 0.911 and 0.918 in predictions of the SF-36 PCS and SF-36 MCS score.^{23,32} Additionally, The SF-12 is one of the most widely used instruments for assessing self-reported HRQOL.³³

5.3.3 Secondary Outcomes: Persons with Memory Loss (PWML)

Secondary outcomes are designed to enable us to examine potential mechanisms of action based on our quality of life conceptual framework (Figure 2). Based on our pilot work and conceptual models of quality of life in person with memory loss and caregivers,^{14,34} we hypothesize that participation in Moving Together may result in improved quality of life for persons with memory loss through the domains of emotional well-being, social relationships (reduced social isolation), physical function (improved mobility), and/or improved cognitive function. In caregivers, we hypothesize that improved quality of life may be due to the changes observed in their loved ones (well-being, isolation, mobility, cognitive function) as well as changes in themselves (improved self-efficacy, reduced burden, reduced social isolation, improved ability to self-regulate, positive affect).

- Well-being: We will measure well-being using the Neuro-QOL v1.0 Positive Affect and Well-Being Short Form.²⁰ It includes 9 items (e.g. sense of well-being, feeling hopeful, life was satisfying, etc.) with 5-point responses from never (1), to always (5). Scores may range from 9 to 45, with higher scores reflecting greater feelings of well-being. Persons Living with Memory Loss will answer for themselves. All Neuro-QOL measures, including Neuro-QOL Short Form v1.0 – Lower Extremity Function – Mobility listed below, have been shown to have internal consistency (Cronbach α) ranging from 0.85 to .97.²⁰
- Social isolation: We will measure social isolation using the PROMIS v2.0 Social Isolation Scale, which consists of 4 items (feeling left out, people barely know me, feeling isolated, people are around but not with me) that are rated as 1 (never), 2 (rarely), 3 (sometimes), 4 (usually), or 5 (always). Scores may range from 4 to 20, with higher

scores reflecting greater social isolation. Persons living with memory loss will answer for themselves. The PROMIS Social Isolation scale demonstrated high reliability coefficients (>0.98), and item-total correlations were moderate.²¹ Based on qualitative results from previous PLIÉ studies,¹⁵ we anticipate that social isolation will decline in Moving Together participants.

- **Mobility:** We will measure mobility using the Neuro-QOL Short Form v1.0 – Lower Extremity Function – Mobility.²⁰ It includes 8 items for functional mobility (e.g. getting on and off the toilet, getting in and out of a car, getting out of bed into a chair etc.) Responses on a 5-point Likert scale from ‘without any difficulty’ (5) to ‘unable to do’ (1) yield a score range from 8 to 40, with higher scores indicating better mobility. As part of the Neuro-QOL measures, the Neuro-QOL Short Form v1.0 – Lower Extremity Function – Mobility has been shown to have internal consistency (Cronbach α) ranging from 0.85 to .97. To confirm the responses of persons living with memory loss, we plan to ask caregivers to answer these questions regarding their loved ones.
- **Cognitive function:** We will measure cognitive function in PWML using the telephone version of the Montreal Cognitive Assessment (t-MoCA). The t-MoCA is extracted from the original face-to-face MoCA and uses items not requiring the use of a pencil and paper or visual stimulus.²² Scores range from 0 to 22 with lower scores indicating more severe impairment.

5.3.4 Secondary Outcomes: Caregivers (CGs)

Consistent with our conceptual framework (Figure 2), we hypothesize that caregiver quality of life will be associated with factors related to the person with dementia as well as factors related to the caregiver.

Factors related to PWML: Several factors in the person with memory loss contribute to quality of life in the caregiver, including the quality of the relationship, changes in the person with dementia especially related to cognition and personality, and the physical demands of caregiving.³⁴ As noted in the preceding section, we will ask caregivers to rate their loved ones’ level of difficulty with **mobility** to determine whether changes in this scale are associated with changes in caregiver quality of life. We also will use the measures in PWML described above to determine whether self-perceptions of their own **well-being** and **social isolation** or objectively measured **cognitive function** are associated with caregiver quality of life.

Factors related to the caregiver: In addition to our primary outcome of caregiver QOL assessed using the SF-12,²³ we will administer several other questionnaires.

- **Caregiver Healthy Days:** We will use the Center for Disease Control and Prevention 4-item Healthy Days Core Module as a secondary measure of CG self-rated health.²⁴ This includes a question about overall health status (same as first item on SF-12) and 3 questions about the number of days during the past 30 days that physical or mental health was not good or poor physical or mental health kept from doing usual activities. The full “Healthy Days Measures” consists of 14 items spanning physical and mental health and demonstrated an internal consistency of .81. Higher scores indicate worse health status.
- **Caregiver self-efficacy:** We will use the GAIN in Alzheimer Care Instrument to assess

caregiver-self efficacy.²⁵ Internal consistency of GAIN by Cronbach's was 0.89 and test-retest reliability (2 weeks) by Intraclass Correlation Coefficient was 0.70. The instrument consists of 10-items (e.g., increased my self-awareness, increased my knowledge and skills in dementia care) using a Likert scale from 0 (disagree a lot) to 4 (agree a lot), with scores ranging from 0 to 40. Higher scores signify higher gains in self-efficacy.

- Caregiver burden: We will use the Zarit Burden Interview (6-item version) to measure caregiver burden.²⁶ The Zarit Burden Interview is one of the most widely used assessments for caregiver burden covering areas including (e.g., caregiver's health, psychological well-being, finances, social life, and the relationship between the caregiver and the person with dementia.³⁵ The 6-item version has emerged as the most optimal short version and has demonstrated high correlation with Center for Epidemiological Studies Depression Scale (CES-D) scores and does not significantly differ from the original ZBI (all Bonferroni adjusted $ps>0.05$).²⁶ The responses to every item are in 5-point Likert scale from 0 (never) to 4 (nearly always). The overall burden is assessed by the total score of all items, with scores ranging from 0 to 20, and a higher score indicating a greater caregiver burden.³⁶
- Caregiver social isolation: We will measure social isolation using the PROMIS v2.0 social isolation scale,²¹ which consists of 4 items (feeling left out, people barely know me, feeling isolated, people are around but not with me) that are rated as 1 (never), 2 (rarely), 3 (sometimes), 4 (usually), or 5 (always). The PROMIS Social Isolation scale has demonstrated high reliability coefficients (>0.98), and moderate item-total correlations.²¹ Scores may range from 4 to 20, with higher scores reflecting greater social isolation.
- Caregiver self-regulation: We will use the Abbreviated MAIA-2 – Self-regulation subscale to measure self-regulation.^{27,37} The MAIA-2 – Self-regulation subscale is designed to assess ability to regulate distress by attention to body sensations (e.g., when I feel overwhelmed, I can find a calm place inside). It includes 4 items rated on a 6-point Likert scale from 0 (Never) to 5 (Always). Scores range from 0-20. Higher scores indicate greater self-regulation.
- Caregiver positive affect: We will use the Positive States of Mind scale to measure positive affect.²⁸ The Positive States of Mind scale is designed to assess types of positive mood (e.g., focused attention, productivity, responsible caregiving, etc.). This scale consists of 6-items using a 4-point Likert scale from 0 (Unable to have it) to 3 (Have it Easily). Each subject receives six specific state scores and scores can be added up for a total positive state score. Total scores may range from 0 to 18, with higher scores reflecting more positive affect.
- Caregiver sleep: We will use 3 items from the Symptom Checklist to measure caregiver sleep.³⁸ The Symptom Checklist-90-Revised is a 90-item self-report questionnaire often used to assess global psychological distress.³⁹ The 3 sleep items (trouble falling asleep, awakening in the early morning, and sleep that is restless or disturbed) were shown to be predictive of overall poor sleep, as measured by an elevated Pittsburgh Sleep Quality Index score and probable insomnia disorder according to DSM-5 diagnostic criteria.³⁸ Responses use a 5-point Likert scale ranging from 0 (Never) to 4 (Extremely) with scores ranging from 0 to 12. Higher scores indicate more severe sleep problems.
- PWML sleep: We will use the same assessment measure listed above to assess PWML sleep.³⁸ Caregivers will answer these questions regarding their loved ones

- **PWML mobility:** We will use the Neuro-QOL Short Form v1.0 – Lower Extremity Function – Mobility²⁰ to measure mobility in PLML based on caregiver report. As described above, it includes 8 items for functional mobility (e.g. getting on and off the toilet, getting in and out of a car, getting out of bed into a chair, etc.). The instrument has been determined to have good reliability Responses on a 5-point Likert scale from ‘without any difficulty’ (5) to ‘unable to do’ (1) yield a score range from 8 to 40, with higher scores indicating better mobility.
- **PWML cognitive function:** We will use a modified version of the Cognitive Function Instrument (CFI) to measure cognitive function in PWML based on caregiver report. The CFI was developed to detect early changes in cognitive and functional changes.⁴⁰ The original scale included 14 items that asked about decline in cognitive function (e.g., memory, tendency to repeat questions, misplacing things, etc.) compared to 1 year ago with responses of yes (1), no (0) or maybe (0.5). Results demonstrated reasonable test-retest reliability at three months for both subject and study partner responses.⁴¹ The modified version excludes 3 items (driving, managing money, work); asks about change in the past 3 months (to match the duration of our study); and uses a 5-point Likert scale from 1 (a lot worse) to 5 (a lot better). Total scores may range from 5 to 55, with higher scores indicating improved cognitive abilities and function.

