3 STUDY DESIGN

We will perform a randomized, controlled trial (RCT) with a 12-week delayed start control group in 224 dyads (Figure 1). Dyads will be enrolled in cohorts of 16. After being screened for eligibility, consented (V0), and completing baseline assessments (V1), dyads will be randomly assigned to immediate start intervention ($n=8$ dyads/cohort) or delayed start control ($n=8$ dyads/cohort) groups. A total of 14 cohorts will be enrolled to achieve our target sample size of 224 dyads. Immediate start groups will participate in the livestreaming Moving Together program from their homes for 1 hour, 2 days/week, for 12 weeks, while delayed start groups engage in usual activities. Twelve-week follow-up assessments will be performed in both groups (V2). The immediate start group will then be invited to participate in maintenance classes on a paid basis, while the delayed start group participates in the Moving Together program for 1 hour, 2 days/week for 12 weeks. Twenty-four week follow-up assessments will then be performed in both groups (V3), and the delayed start group will be invited to join the maintenance classes on a paid basis. Those who participate in the maintenance classes will be invited to provide ongoing feedback.

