5.2.3 Baseline and Follow-Up Assessments (V1, V2, V3)

All participants will complete the assessments listed below at baseline (V1), 12 weeks (V2) and 24 weeks (V3). Detailed descriptions of each measure are provided below, in section 5.3.

Persons with Memory Loss (PWML) outcome measures:

- Primary:
 - Quality of life (Quality of Life in Alzheimer's Disease Scale, QOL-AD)¹⁹
- Secondary:
 - Well-being (Neuro-QOL v1.0 Positive Affect and Well-Being Short Form)²⁰
 - Social isolation (PROMIS v2.0 social isolation scale)²¹
 - Mobility (Neuro-QOL Short Form V1.0 - Lower Extremity Function - Mobility)²⁰
 - Cognitive function (telephone Montreal Cognitive Assessment, t-MoCA)²²

Caregivers outcome measures:

- Primary:
 - SF-12²³
- Secondary:
 - Healthy Days (CDC)²⁴
 - Caregiver self-efficacy (GAIN in Alzheimer Care Instrument)²⁵
 - Caregiver burden (Zarit Burden Interview, 6-item version)²⁶
 - Caregiver social isolation (PROMIS v2.0 social isolation scale)²¹
 - Caregiver self-regulation (Abbreviated MAIA-2 self-regulation subscale)²⁷
 - Caregiver positive affect (Positive States of Mind)²⁸
 - Caregiver sleep (Symptom Checklist, 3 items)
 - PWML sleep (Symptom Checklist, 3 items)
 - PWML mobility (Neuro-QOL Short Form V1.0 - Lower Extremity Function - Mobility)²⁰
 - PWML cognitive function (Cognitive Function Instrument – Modified)

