10.3 Data Analyses

We will examine distributions of all variables to assess for missingness, outlier values or skewed distributions using standard techniques (e.g., means, medians, standard deviations, ranges, tables, graphical techniques). We will assess balance between the immediate and delayed start groups by comparing baseline characteristics (e.g., means \pm SD, N [%]). If meaningful differences occur by chance, we will perform sensitivity analyses adjusting for these differences.

Our primary analytic approach will be linear mixed models (LMMs) with terms included for group, time, and group*time interaction with random intercepts and slopes. This approach will enable efficient estimation of change in primary outcomes over time while including all participants randomized (intent-to-treat) and accounting for baseline values and correlations between repeated measures over time. Milestone 1a will determine if there is a significant group*time interaction for our primary outcome of quality of life, with separate analyses performed for PWML and CGs. Milestone 1b will involve exploratory analyses to examine potential mechanisms of action. These will include using PROCESS to assess for indirect effects (mediation) and contingent effects (moderation) based on baseline characteristics of our study participants (e.g., age, sex, caregiving relationship) and changes in secondary outcomes (e.g., mobility, well-being, isolation). Exploratory analyses also will examine the impact of 'dose' (based on class attendance), and sensitivity analyses will be restricted to those with high compliance ($\geq 75\%$ class attendance). For covariates that have more than 10% missing data, we will consider using multiple imputation.

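### The modified CFI is already a 3-month change rating; a linear V1–V3 group-by-time model, if applied to it, can show a benefit as harm or as no effect

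*Combined protocol and SAP*

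**What the plan says.** Section 5.3.4 describes the modified CFI, completed by the caregiver about the person with memory loss. It "asks about change in the past 3 months (to match the duration of our study"). For its response options, the instrument "uses a 5-point Likert scale from 1 (a lot worse) to 5 (a lot better"). Higher totals mean improvement.

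Section 5.2.3 lists it among the caregiver secondary outcomes, as "PWML cognitive function (Cognitive Function Instrument – Modified"). Its timing is the same as for the other measures: "All participants will complete the assessments listed below at baseline (V1), 12 weeks (V2) and 24 weeks (V3").

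Under section 3, the immediate arm takes classes in the first 12 weeks. After V2 that arm is offered paid maintenance classes, "while the delayed start group participates in the Moving Together program for 1 hour, 2 days/week for 12 weeks".

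Section 10.3 gives one longitudinal model: "linear mixed models (LMMs) with terms included for group, time, and group*time interaction with random intercepts and slopes". The surrounding text speaks of change in the primary outcomes and places the interaction test on quality of life. It does not give the coding of time, the visits that enter the test, a model for secondary outcomes, or a rule for an outcome that is itself a rating of change.

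**The concern.** Most outcomes in this trial measure status at a visit, so a model over visits estimates change. The modified CFI does not work that way. Its V2 score alone is the caregiver's account of change over weeks 0–12, the only period in which one arm has the program and the other does not. Its V1 score describes a period before randomization. Its V3 score describes weeks 12–24, when the delayed arm is in classes and the immediate arm has finished them.

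A slope fitted through these three scores estimates a change in the rate of change. It also compares the arms mainly over the period when the control arm is being treated. If the section 10.3 model were carried over to the CFI with linear time, a program that helps both arms equally could be reported as worse than control, or as having no effect. Left unspecified, the choice between analyses that can give opposite signs would be made after the data are seen.

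**Working it through.** **Inputs from the documents.** Two-sided alpha 0.05, 112 per arm, standardized effect 0.375 and 20% attrition (section 10.2); V1, V2 and V3 at 0, 12 and 24 weeks (5.2.3); delayed arm treated between V2 and V3 (section 3); response scale 1 to 5 (5.3.4).

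**Assumptions, not in the documents.** The program raises the 3-month rating by D during an arm's own class period. In weeks 12–24 the immediate arm's rating stands at fD above background, where f = 0 means that the gain is held without further improvement and f = 1 means that improvement continues at the full rate. Both arms respond equally. Scores have SD 1 and the same correlation ρ between any two visits. Data are complete and the normal approximation is used.

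**Step 1: the plan's own figure.** The plan gives no figure for the CFI. Its sample size reproduces: 0.375 / √(2/112) = 2.81, and Φ(2.81 − 1.96) = 0.80. Attrition of 20% leaves 0.8 × 112 = 89.6, about 90 per arm.

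**Step 2: expected interaction.** Departures from background at V1, V2 and V3 are (0, D, fD) in the immediate arm and (0, 0, D) in the delayed arm. With visits coded 0, 1, 2, the least-squares slope has weights (−½, 0, +½). The V2 rating, the only one that covers the randomized comparison, gets weight zero.

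- Immediate slope: fD/2. Delayed slope: D/2.
- Interaction: (f − 1)D/2 per 12 weeks.
- f = 0 gives −0.5D; f = 0.5 gives −0.25D; f = 1 gives 0.

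**Step 3: an example in points.** "The modified version excludes 3 items (driving, managing money, work") from the original 14 items, which leaves 11, so no change on every item scores 11 × 3 = 33. Take a background of −2 and D = +4:

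| | V1 | V2 | V3 | Slope |
|---|---|---|---|---|
| Immediate | 31 | 35 | 31 | 0 |
| Delayed | 31 | 31 | 35 | +2 |

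The interaction is −2 points per 12 weeks, although both arms gain 4 points from the program. With categorical time the contrast against V1 is +4 at V2 and −4 at V3.

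The same history on a status scale, with a background decline of 2 per period, gives levels (0, +2, 0) and (0, −2, 0). Both slopes are 0 and the interaction is 0. In this case the negative sign comes from the change-rating format and not from the delayed-start design alone.

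**Step 4: probability of a significant result in the wrong direction.** The interaction is half the between-arm difference in V3 − V1, so z = (1 − f)D / √(4(1 − ρ)/n), and the probability is Φ(z − 1.96). With ρ = 0.4, 4(1 − ρ) = 2.4.

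| D | f | n per arm | z | Wrong direction |
|---|---|---|---|---|
| 0.4 | 0 | 112 | 0.4/0.146 = 2.73 | 78% |
| 0.4 | 0 | 90 | 0.4/0.163 = 2.45 | 69% |
| 0.4 | 0.5 | 90 | 0.2/0.163 = 1.22 | 23% |

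At the plan's effect of 0.375 with 112 per arm and f = 0, simulation (4,000 runs per setting) gave 51%, 66%, 80% and 95% for ρ = 0, 0.3, 0.5 and 0.7. Twenty mixed models fitted to simulated data with D = 0.375 averaged −0.17 for the linear interaction (expected −0.19); with categorical time they gave +0.40 at V2 and −0.34 at V3. Some of those fits had convergence warnings, so they confirm the sign and little more.

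**Step 5: the alternative.** The V2 score adjusted for V1 estimates +D with variance 2(1 − ρ²)/n. For D = 0.4, ρ = 0.4 and 112 per arm, the SE is √(1.68/112) = 0.122, z = 3.27 and power is 90%. The V2 − V1 contrast also estimates +D, but its variance is larger by 2(1 − ρ)/(1 − ρ²) = 2/(1 + ρ). That is 1.43 at ρ = 0.4, and 1.25 to 1.67 for ρ from 0.6 to 0.2.

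**The case against.** The strongest reply is that the plan never says it will do this. Section 10.3 words the mixed model for the primary outcomes and states no model for any secondary outcome. A reader might infer that a V1–V3 slope is the planned CFI analysis; the documents do not establish that. They do give only this one longitudinal model, and random slopes with a residual term need more than two visits, which points toward V1–V3. It remains an inference.

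Second, the wrong sign needs linear time over three visits, or reliance on the V3 contrast. Other text leans toward a 12-week comparison: section 10.2 bases power on an unpaired t-test, and the remark in 5.3.4 about matching the study's duration fits a V2 reading. On V1–V2 the sign is right. This stands, and it is why the point is conditional.

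Third, a reader might conclude that the trial would report a working program as inferior. That goes too far. The interaction depends on what the immediate arm does in weeks 12–24, when maintenance classes are on offer, and it vanishes if improvement continues at the full rate.

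Fourth, the efficiency loss of a V2 − V1 contrast holds for any change score compared with baseline adjustment. That is correct, so it is not counted as a CFI-specific fault.

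Fifth, a reader might take the CFI to be a named mediator. Section 10.3 refers to changes in secondary outcomes, with mobility, well-being and isolation as examples, and section 5.3.4 points to objectively measured cognition when it discusses links with caregiver quality of life. Use of the CFI in mediation is possible but not stated.

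Finally, this is one of ten caregiver-completed secondary outcomes, and cognition is also tested directly with the t-MoCA. That limits the consequence but does not make a slope suitable for a transition rating.

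**Conclusion.** The concern holds in conditional form. The modified CFI is a transition rating, and the one longitudinal model in the plan does not suit it when time is linear over V1–V3. For f between 0 and 1, with equal effects in the two arms, the interaction is never positive for a beneficial program.

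The probabilities in the working rest on assumed values of D, ρ and f. The range from 78% down to 23% shows how strongly the risk depends on sample size and on continued improvement after week 12; at f = 1 the expected interaction is zero and the benefit is simply missed. The finding is that a benefit can appear as harm or as no effect, not that it will.

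The sample size and the quality-of-life conclusions are untouched. The change is still worth making, because a clearly better analysis is available at no cost.

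**What to change.** Add to section 10.3:

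- The modified CFI is analysed as the between-arm difference in the V2 score, with the V1 score as a covariate, because the V2 score already records change over weeks 0–12.
- No V1–V3 slope and no change from baseline is fitted to it.
- V3 scores are reported descriptively by arm.
- If the CFI enters a mediation model, the V2 score itself is used, not its difference from V1.

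The same section should say which model applies to the other secondary outcomes, so that none is left to inference. While 5.3.4 is open, check the stated score range as a separate matter: 11 items scored 1 to 5 give 11 to 55, not a minimum of 5.

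The cost is wording only. No new data, visits or participants are needed.
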